---

**The following Amendment(s) and Administrative Changes are included in this amended protocol:**

Amendment No.	Date of Amendment	Local Amendment No.	Date of local Amendment
1	[REDACTED]		
2	[REDACTED]		
3	[REDACTED]		
4	[REDACTED]		
5	[REDACTED]		
6	[REDACTED]		
Administrative change No.	Date of Administrative Change	Local Administrative change No.	Date of local Administrative Change
1	[REDACTED]		
2	[REDACTED]		

## PROTOCOL SYNOPSIS

---

### **A Phase I, Open Label, Multi-centre Study of AZD2281 Administered Orally in Combination with Cisplatin, to Assess the Safety and Tolerability in Patients with Advanced Solid Tumours**

---

#### **Study centre(s), type and number of patients planned**

This will be a multi-centre study run from approximately 4 investigational sites in the USA and Spain. The maximum tolerated dose of AZD2281 (or the highest well tolerated dose explored) that can be combined with cisplatin will be established in patients with advanced solid tumours. Depending on the doses of AZD2281 explored it is expected that 60 patients will be enrolled.

#### **Study period**

Estimated date of first patient enrolled

[REDACTED]

Estimated date of last patient completed

[REDACTED]

#### **Phase of development**

I

#### **Objectives**

- The primary objective is to determine the safety and tolerability of twice daily doses of AZD2281 when administered in combination with cisplatin to patients with advanced solid tumours.

#### **The secondary objectives of the study are:**

1. To compare exposure to AZD2281 when given alone and in combination with cisplatin. (Only in patients receiving continuous dosing of AZD2281)
2. To make a preliminary assessment of the anti-tumour activity of AZD2281 when given in combination with cisplatin, by measuring overall objective response rate.

#### **The exploratory objectives of the study are:**

- To obtain an optional blood sample for DNA extraction for future pharmacogenetic analysis and other potential correlative markers of the activity of AZD2281 and drugs taken in combination with AZD2281 (ie, cisplatin).

The exploratory analyses will be reported separately

## Study design

The study is a non-randomised, open label, Phase I dose finding study, to determine the maximum tolerated dose of AZD2281 that can be combined with cisplatin in patients with advanced solid tumours.

Each cohort will comprise a minimum of 3 evaluable patients. If 1 patient from the initial 3 experiences DLT the cohort will be expanded to at least 6 patients. It is expected that 60 patients will be enrolled.

Once the desired doses or MTD of the combination therapy has been determined (or the highest dose level has been explored) the cohort will be expanded to ensure that there are 6 evaluable patients who have completed four cycles of combination treatment.

The Maximum Tolerated Dose (MTD) is defined as the prior dose level below the drug-combination that causes DLT, in at least 2 patients in a cohort of up to 6 patients. If toxicity is equivocal and it is not possible to determine a MTD with certainty, further cohorts of at least three patients may be recruited to allow an informed decision to be taken about further dose escalations with AZD2281.

The dose escalation may continue until the MTD is established; however the highest dose to be explored will be 400 mg bd. Intra-patient dose escalation is not permitted.

If continuous dosing is not tolerated, intermittent dosing will be explored. An intermittent dosing cohort will be opened to enrol 12 patients at the following dose:

- AZD2281 at 100 mg bd for days 1-10 of a 21 day cycle with 75 mg/m^2 of cisplatin on day 1 of a 21 day cycle
- Day 1 of cisplatin and day 1 of AZD2281 are the same day

In the event that the initial intermittent dose cohort is not tolerated, further cohorts may be investigated with a starting dose of AZD2281 at 50 mg bd for days 1-5 of a 21-day cycle with 75 mg/m^2 of cisplatin on day 1 of a 21-day cycle.

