#### **4.1.1 Stopping criteria for dose escalation**

AZD2281 will commence at 50 mg twice-daily in cohort 1, then increase to 100 mg twice-daily and 200 mg twice-daily. A further dose-escalation of AZD2281 to 400 mg twice-daily may be considered following review of the data. The dose of cisplatin will be 75 mg/m^2.

Dose-escalation of AZD2281 will stop if Dose Limiting Toxicity of the drug-combination occurs. At least three patients treated in a cohort must undergo repeated safety evaluations, up to and including Day 21, before enrolment of patients in the next dose cohort begins. Decisions to escalate to the next level, or, when appropriate, to an intermittent level, will be made jointly by the investigator and sponsor's Responsible Medical Officer based on review of all the available data.

If one patient in a cohort of 3 evaluable patients experiences a dose-limiting toxicity (DLT) during the first cycle that is considered related to combination-therapy, the cohort will be expanded to at least 6 patients.

In the continuous dosing schedule, Pharmacokinetic (PK) evaluations will be performed and may be utilised to guide appropriate changes to the regimen, if indicated. Cisplatin has the potential to cause nephrotoxicity which may affect clearance of other agents, including AZD2281.

Table 2 shows the continuous dosing escalation strategy to be adopted:

**Table 2** Proposed dose escalation schedule for the continuous dosing regimens

Cohort	Number of patients recruited	Cisplatin dose Q21d	AZD2281 dose	Schedule
1	3 – 6	75 mg/m 	50 mg bid	Continuous
2	3 – 6	75 mg/m 	100 mg bid	Continuous
3	3 – 6	75 mg/m 	200 mg bid	Continuous

In the event that the continuous dosing regimens are not tolerated, intermittent dosing regimens will be explored.

Table 3 shows the intermittent dosing strategy to be adopted:

**Table 3** Proposed dose schedule for the intermittent dosing regimens

Cohort	Number of patients recruited	Cisplatin dose Q21d	AZD2281 dose	Schedule
4	12	75 mg/m 	100 mg bid	Day 1-10 of the 21-day cycle
5	4-12	75 mg/m 	50 mg bid	Day 1-5 of the 21-day cycle
	4-12	75 mg/m 	50 mg bid	Day 1-3 of the 21-day cycle
	4-12	60 mg/m 	50 mg bid	Day 1-5 of the 21-day cycle
	4-12	75 mg/m 	50 mg bid	Day 2-6 of the 21-day cycle
	4-12	75 mg/m 	100 mg bid	Day 1-5 of the 21-day cycle

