#### **4.1.3 Maximum Tolerated Dose**

The Maximum Tolerated Dose (MTD) is defined as the prior dose level below the drug-combination that causes DLT, in at least 2 patients in a cohort of at least 6 patients.

If, at any dose level, a patient fails to complete cycle 1 for reasons other than DLT, that patient is deemed unevaluable for determining the MTD and may be replaced. Such a patient will be included in the evaluation of toxicity and efficacy.

[figure not shown]
Exploration of different combination dosing regimens may be investigated to provide a tolerated dose of AZD2281 combined with cisplatin which can be investigated in further studies, however the highest dose to be explored will be 400 mg bid. (The MTD established in the monotherapy Phase I study).

**Figure 2** Study flow chart - Continuous dosing schedule

\* PK blood draws will not be performed for patients enrolled into an intermittent dosing cohort

**Figure 3** Study flow chart - Intermittent dosing schedule

Note: Patients can continue treatment for as long as they are benefiting and are free from significant toxicity. After patients complete 6 cycles of cisplatin based therapy, cisplatin may be discontinued and AZD2281 alone may be continued at the optimal monotherapy dose (i.e. 400 mg bid) at the investigators discretion. See Section 4.2.3 and Table 5 for full details.

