#### **7.4.5 Determination of sample size**

The primary objective of the study is safety and tolerability of ascending doses of AZD2281 in combination with cisplatin. The total number of patients has, therefore, been based on the desire to obtain adequate safety and tolerability data whilst exposing as few patients as possible to the study treatment and procedures. A patient will be defined as evaluable for safety review if they complete at least 1 cycle of cisplatin (3 weeks) and also receive at least 75% of either continuous or intermittent daily treatment of AZD2281 or they experience a DLT prior to completing 21 days of either continuous or intermittent treatment. If there are fewer than 3 evaluable patients in a given cohort then further patients will be recruited to the cohort until there are at least 3 evaluable patients. Once the dose or MTD has been determined (or the highest dose level has been explored) the cohort will be expanded to ensure that there are 6 evaluable patients who have completed four cycles of treatment.

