### **7.5 Interim analyses**

Safety, tolerability and PK data (if decided needed) from each cohort will be reviewed on an ongoing basis by the safety monitoring committee (see Section [7.6](#)).

At least 3 evaluable patients in a given cohort must be treated, followed up and assessed for 21 days prior to recruiting patients into subsequent cohorts. In addition, the first patient in

each cohort will have to provide acceptable Day 7 safety data before further patients can be included.

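### After one DLT in the first three, the cohort grows to at least six patients, not six evaluable patients, so an escalation decision can rest on 1 DLT in 5 or, less often, 4 evaluable patients

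*Protocol*

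**What the plan says.** The starting cohort is defined in evaluable patients: "Each cohort will comprise a minimum of 3 evaluable patients" (Synopsis, Study design; repeated in 4.1). The expansion is not: "If 1 patient from the initial 3 experiences DLT the cohort will be expanded to at least 6 patients". Section 4.1.1 changes unit within one sentence. It begins "If one patient in a cohort of 3 evaluable patients experiences a dose-limiting toxicity (DLT) during the first cycle" and ends "the cohort will be expanded to at least 6 patients". Table 2 sizes each continuous-dosing cohort at 3 to 6 under the column heading "Number of patients recruited".

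Two provisions set an evaluable minimum before the next cohort opens, and both set it at 3:
- Section 7.4.5: "further patients will be recruited to the cohort until there are at least 3 evaluable patients".
- Section 7.5: "At least 3 evaluable patients in a given cohort must be treated, followed up and assessed for 21 days", before the next cohort is recruited.

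A minimum of 6 evaluable patients with four completed cycles does exist (Synopsis, 4.1, 4.1.1, 7.4.5). It applies once the desired dose or MTD has been determined, or the highest dose explored.

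On replacement, 4.1.3 says of a patient who does not complete cycle 1 for a reason other than DLT: "that patient is deemed unevaluable for determining the MTD and may be replaced". Section 4.4.6.3 says that patients who withdraw are not replaced.

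Section 7.6 has the safety monitoring committee meet when all evaluable patients in the cohort have completed 21 days. It sets no minimum number for a cohort that has had a DLT.

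**The concern.** The expansion exists to find out whether one DLT in three patients was chance or a sign that the combination is too toxic. Only evaluable patients can answer that, because 4.1.3 excludes the others from the MTD determination. If an added patient stops early for another reason, or takes less than 75% of the planned AZD2281 without a DLT, the cohort still holds six patients while its denominator for the decision has shrunk. The 3-evaluable gate was met before the expansion began, so it gives no protection here.

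The gap affects dose levels passed on the way up, in the one situation where a toxicity signal has already appeared. It makes it somewhat more likely that a too-toxic level is passed.

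**Working it through.** **Plan's own figure.** The Protocol states no operating characteristics for the escalation rule, so there is nothing to reproduce.

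**Inputs from the Protocol.** 3 evaluable patients to start; 3 more patients added after 1 DLT; 2 DLTs define a level above the MTD.

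**Assumed inputs, which the Protocol does not give.**
- True DLT probability p: 33%, with 50% as a second case.
- Probability d that an added patient is unevaluable: 10%, 20% or 30%. Write q = 1 − d.
- No replacement, exactly 3 patients added, patients independent, and escalation whenever fewer than 2 DLTs are seen.

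**Step 1: how many of the 3 added patients are evaluable (binomial).**

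| d | 6 evaluable in total | 5 | 4 | 3 | Fewer than 6 (1 − q³) |
|---|---|---|---|---|---|
| 10% | 72.9% | 24.3% | 2.7% | 0.1% | 1 − 0.729 = 27% |
| 20% | 51.2% | 38.4% | 9.6% | 0.8% | 1 − 0.512 = 49% |
| 30% | 34.3% | 44.1% | 18.9% | 2.7% | 1 − 0.343 = 66% |

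The shortfall is mostly 5 evaluable patients instead of 6, and sometimes 4.

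**Step 2: chance of escalating when k added patients are evaluable.**
P = (1 − p)³ + 3p(1 − p)² × (1 − p)^k

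At p = 0.33, (1 − p)³ = 0.301 and 3p(1 − p)² = 0.444.
- k = 3: 0.301 + 0.444 × 0.301 = 0.434
- k = 2: 0.301 + 0.444 × 0.449 = 0.500
- k = 1: 0.301 + 0.444 × 0.670 = 0.599

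**Step 3: average over k.** Each added patient shows an evaluable DLT with probability qp, so
P = (1 − p)³ + 3p(1 − p)² × (1 − qp)³

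| d | p = 33% | Rise from 43.4% | p = 50% | Rise from 17.2% |
|---|---|---|---|---|
| 10% | 0.301 + 0.444 × 0.703³ = 45.5% | 2.1 points | 18.7% | 1.6 points |
| 20% | 0.301 + 0.444 × 0.736³ = 47.8% | 4.4 points | 20.6% | 3.4 points |
| 30% | 0.301 + 0.444 × 0.769³ = 50.3% | 6.8 points | 22.8% | 5.6 points |

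**Step 4: precision.** The upper 95% Clopper-Pearson limit for the DLT rate is 64.1% for 1/6, 71.6% for 1/5 and 80.6% for 1/4. Six patients are already imprecise; five or four are more so.

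**The case against.** **It may be only a missing word.** Section 4.1.1 starts its expansion sentence from evaluable patients, and 4.1.3 excludes unevaluable patients from the MTD. Read together, six evaluable patients were probably intended. That is fair evidence of intent. However, Table 2 counts recruited patients, 7.4.5 tops up only to 3, and 4.4.6.3 refuses replacement after withdrawal. Following the text as written does not require six.

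**Escalation is not automatic.** A reader might infer that 1 DLT in an expanded cohort satisfies every rule for moving up. The Protocol does not say so. That 1 in 6 permits escalation is inferred from the two-DLT definition of the MTD, while 4.1.1 also says escalation stops if DLT of the combination occurs. Section 7.6 leaves the decision to a committee with at least 3 physicians, and 4.1.3 keeps unevaluable patients in the toxicity evaluation. There is also provision for further cohorts of three when toxicity is equivocal: optional in the Synopsis, firmer in 4.1. Its trigger in both places is a judgement about toxicity, not a count of evaluable patients. These provisions allow a top-up; none requires one because fewer than 6 were evaluable.

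**The selected dose is protected.** A reader might infer that 3 is the only evaluable minimum anywhere. It is not, because the selected dose needs 6 evaluable patients with four cycles. The point concerns only the levels passed before that.

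**Escalating on 1 in 3 is remote.** A reader might also infer that the expansion could add no information at all. That needs all three added patients to be unevaluable, with probability 0.1% to 2.7% for d of 10% to 30%.

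**The size is at the upper end.** The calculation assumes no replacement although 4.1.3 allows it, and escalation without committee restraint. A patient with a DLT before dropping out is evaluable, which also limits the loss. One consideration runs the other way. Mid-cycle Grade 3 thrombocytopenia is not among the DLTs in 4.1.2, yet Table 6, footnote a, holds the remaining AZD2281 for that cycle. If this starts before about day 16 (75% of 21 days = 15.75) on continuous dosing, the patient may be neither a DLT nor evaluable. Unevaluable patients may therefore not be a random subset; the figures do not model this.

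**Conclusion.** The point holds in a limited form. After 1 DLT in the first 3 evaluable patients, the Protocol allows an escalation decision on 1 in 5, or less often 1 in 4, evaluable patients. No stated rule requires a top-up to 6 first. The shortfall would be common (27% to 66% of expansions for unevaluability of 10% to 30%), but its average effect is modest: a rise of about 2 to 7 points in the chance of escalating at a true DLT rate of 33%, from 43% to about 46% to 50%. Both ranges rest on assumed rates, no replacement, and escalation whenever fewer than 2 DLTs are seen. The documents do not support reading this as a licence to escalate on 1 in 3, or as escalation without committee judgement. It is still worth correcting, because safety and tolerability are the primary objective and the change is small.

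**What to change.** 1. In the Synopsis (Study design), 4.1 and 4.1.1, state the post-DLT expansion as at least 6 evaluable patients, and make the Table 2 column heading consistent with that.
2. In 7.4.5 and 7.5, add that a cohort with a DLT among its first 3 evaluable patients is topped up to 6 evaluable patients before any escalation decision, unless 2 DLTs have already occurred.
3. Reconcile 4.1.3, where unevaluable patients may be replaced, with 4.4.6.3, where withdrawn patients are not.
4. Reconcile the MTD denominators: 2 DLTs in up to 6 patients (Synopsis, 4.1) against 2 DLTs in at least 6 (4.1.3). As they stand, 2 DLTs among 4 patients meet one definition and not the other.

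The cost is wording plus an occasional replacement patient. Reaching 3 evaluable added patients takes on average 3/q recruits: 3.3, 3.8 or 4.3 at 10%, 20% or 30% unevaluability. That is about 0.3 to 1.3 extra patients per expanded cohort, and fewer where a second DLT ends recruitment. Each replacement also needs 21 days of follow-up, so the decision in a cohort that had a DLT may come somewhat later.

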## Investigational product, dosage and mode of administration

The doses of AZD2281 used in this study will be made up from the available 50 mg capsule strengths.

In all cycles, AZD2281 will be administered orally twice-daily on either a continuous or intermittent basis. Cisplatin will be administered on Day 1 of a 21-day cycle. On Day 1 cisplatin will be administered 2 hours after the first AZD2281 administration.

For the continuous dosing regimens, a single dose of AZD2281 (dose dependent on the cohort) will be given on visit 2 (up to a week before the combination). A full 12-hour plasma PK profile will be taken, this will be repeated when AZD2281 is given together with cisplatin

to enable a comparison of the plasma exposure to AZD2281 alone and repeated in the presence of cisplatin.

For the intermittent dosing regimens, the first dose of AZD2281 will be given on the same day as cisplatin, unless a different dose schedule is advised by the safety monitoring committee. PK blood draws will not be performed for patients enrolled into an intermittent dosing cohort.

### **Duration of treatment**

Each cycle of cisplatin treatment will last 21 days. AZD2281 will be taken twice-daily either continuously (day 1 through day 21) or intermittently. Dosing with AZD2281 will commence in relation to the day that cisplatin is administered, regardless of whether or not there have been any dosing delays or interruptions in the previous cycle.

Combinational treatment with AZD2281 and cisplatin will continue for as long as the Investigator feels that the patient is receiving benefit and is free from significant toxicity. In the event that cisplatin is permanently discontinued on the basis of cisplatin related toxicity, treatment with AZD2281 alone may continue. If the patient does continue on AZD2281 alone, at the discretion of the PI and in consultation with AstraZeneca Study Team Physician, the patient may be dose escalated to receive the optimal monotherapy dose (ie 400 mg bd).

### **Variables**

- **Safety**
  - Adverse events
  - Blood pressure (BP) and Pulse Rate (PR)
  - Body Temperature
  - ECG
  - Haematology
  - Clinical chemistry
  - Urinalysis
  - Physical examination
- **Pharmacokinetic (AZD2281 only)**
  - $C_{max}$ ,  $t_{max}$  and  $AUC_{0-t}$
- **Response**
  - ORR

### **Data cut-off**

There will be a data cut off defined as the time when all patients receiving AZD2281 have been followed for a minimum of 3 months of monotherapy AZD2281 following combination treatment, or there are no more patients remaining on treatment in the study; whichever is the earlier date. At this time point, the clinical study database will close to new data. Patients are however permitted to continue to receive study treatment beyond the closure of the database if, in the opinion of the investigator, they are continuing to receive benefit from treatment with AZD2281. Patients continuing on study treatment will be followed for core safety assessments only (haematology, clinical chemistry, AEs/SAEs and concomitant medications, IMP dosing details). These patients should be followed according to routine clinical practice but visits should take place at least every 8 weeks.

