#### **4.2.6 Final follow up visit**

A final follow-up visit should be conducted 30 days after the last dose of AZD2281. Any serious and/or non-serious AEs ongoing at the time of the Withdrawal Visit or which have occurred during the defined 30-day follow-up period must be followed-up (in accordance with Section 5.10.3). Appropriate safety evaluations should be repeated and/or additional tests performed at any time when clinically indicated, or at the discretion of the Investigator, until resolution, unless, in the Investigator's opinion, the condition is unlikely to resolve due to the patient's underlying disease. The patient may have the 30-day follow-up blood samples taken at a local institution as an alternative to the investigator site, if the patient is too sick to travel. If the patient is lost to follow-up, then this should be noted in the CRF. The assessments to be carried out at the 30 day follow up visit are detailed in the study schedule (Table 4 and Table 5 for the monotherapy phase)

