**Table 4 Study plan (see Section 5 for further details)**

Cycle	0	0	1			2			3,4,5 hq			Withdrawal	30 Day follow up (+/-7days)
Visit Number	1	2*	3	4	5	6	7	8	9	10	11		
Week	-	1	2	3	4	5	6	7	8	9	10		
Study Day	Scr	1-4	8	15	22	29	36	43	50	57	64		
Informed Consent	X a												
Demography	X a												
Confirm eligibility	X c												
Medical / Surgical History	X a												
Physical Examination b	X c		X			X			X j			X	X
Audiometric testing	X j								X j			X j	
Vital signs d	X c		X	X	X	X	X	X	X	X	X	X	
Performance Status	X c		X			X			X d			X	
ECG e	X c				X			X				X	X
Pregnancy test f	X		X										
Tumour assessment p	X								X			X	
Haematology g	X c		X	X	X	X	X	X	X	X	X	X	X
Clinical Chemistry g	X c		X	X	X	X	X	X	X	X	X	X	X
Urinalysis g	X c		X	X	X	X	X	X	X	X	X	X	X
PGx blood sample		X l											
PK blood sampling AZD2281		X i	X i										
Cisplatin infusion			X			X			X h				

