**Table 5**      **Olaparib Monotherapy Phase – see Section 4.2.3**

Visit Type	Olaparib Monotherapy Phase a						Olaparib Monotherapy Treatment Discontinuation	Post Discontinuation Follow-up
	Monotherapy Day 1 b	Monotherapy Day 8 b	Monotherapy Day 15 b	Monotherapy Day 22 b	Monotherapy Day 43 b	Every 6 weeks	N/A	30 days post discontinuation
Visit Window		± 2 days	± 2 days	± 2 days	± 4 days	± 4d	± 3 days	± 3 days
Physical Exam	X				X	X	X	
Vital signs (Includes BP [supine position], pulse rate (PR), body temperature)	X				X	X	X	X
Performance Status	X				X	X	X	X
ECG c							X	
Haematology / Clinical Chemistry	X	X	X	X	X	X	X	X
Tumour Assessment (CT or MRI according to RECIST) d	Tumour assessments at weeks 9 and 18 (± 1 week) and every 12 weeks (± 1 week) thereafter relative to date of cycle 1 day 1 of the combination therapy until disease progression							
Adverse Events	X	X	X	X	X	X	X	X
Concomitant Medications	X	X	X	X	X	X	X	X
Olaparib dispensed / returned e,f	X				X	X	X	

- a All patients should attend study visits until objective disease progression according to RECIST or the patient must discontinue due to unacceptable toxicity as outlined in the protocol
- b Day is relative to the start of olaparib (AZD2281) monotherapy
- c ECGs performed at baseline, completion of chemotherapy, and discontinuation of olaparib maintenance and if clinically indicated at any other time. ECG should be performed once the patient has been in the supine position for at least 5 minutes in each case.
- d RECIST assessment by CT or MRI scans of chest abdomen, pelvis and other regions including chest as clinically indicated for the assessment of disease. Any other sites at which new disease is suspected should also be appropriately imaged If an unscheduled assessment was performed and the patient has not progressed, every attempt should be made to perform the subsequent assessments at their scheduled visits. Mandatory tumour assessments will be performed at baseline, 9 weeks and 18 weeks and every 12 weeks thereafter relative to date of cycle 1 day 1 of combination therapy until disease progression (At withdrawal, RECIST assessment is required, however if the previous RECIST assessment was performed within 6 weeks of withdrawal, the withdrawal RECIST assessment should be performed but can be missed at the discretion of the investigator.

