#### **4.4.6.2 Procedures for Discontinuation of a Patient from Investigational Product**

A patient that decides to discontinue investigational product will always be asked about the reason(s) and the presence of any adverse events. If possible, they will be seen and assessed by an Investigator(s). Adverse events will be followed up (See Sections 5.10.3 and 5.10.4); and all study drugs should be returned by the patient.

Any patient discontinuing investigational product should be seen at 30 days post discontinuation of study treatment for the evaluations outlined in the study schedule. The patient's tumour status should be assessed clinically and, if appropriate, disease progression should be confirmed by radiological assessment. After discontinuation of study medication, the principal Investigator/Sub-Investigator will perform the best possible observation(s), test(s) and evaluation(s) as well as give appropriate medication and all possible measures for the safety of the patient. In addition, they will record on the CRF the date of discontinuation, the reasons, manifestation and treatment at the time of discontinuation. If patients discontinue study treatment, the AstraZeneca monitor must be informed immediately. Patients will be required to attend the treatment discontinuation visit. The patient should return all study medication.

After discontinuation of the study medication at any point in the study, all ongoing AEs or SAEs must be followed until resolution unless, in the Investigator's opinion the condition is unlikely to resolve due to the patients underlying disease, or the patient is lost to follow up

(see Sections 5.10.3 and 5.10.4). All new AEs and SAEs occurring during the 30 calendar days after the last dose of study medication must be reported (if SAEs, they must be reported to AstraZeneca within 24 hours as described in Section 5.10.4) and followed to resolution as above. Patients should be seen at least 30 days after discontinuing study medication to collect and /or complete AE information. Any untoward event occurring subsequent to the 30-day follow-up AE reporting period that the investigator assesses as possibly related to the study medication should also be reported as an AE.

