All dose reductions and interruptions (including any missed doses), and the reasons for the reductions/interruptions are to be recorded in the CRF (up to the data cut-off).

████████████████████  
AZD2281 should be stopped before surgery and re-started after wound has healed following recovery.

No stoppage of AZD2281 is required for any biopsy procedures.

AZD2281 should be discontinued for a minimum of 7 days before a patient undergoes therapeutic palliative radiation treatment.

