### **5.10.3 Recording of adverse events**

#### **Time period for collection of adverse events**

Adverse Events will be collected from time of signed informed consent throughout the treatment period and up to and including the 30-day follow-up period.

SAEs will be recorded from the time of informed consent.

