### **6.6.1 Patient Management Post Data cut-off**

#### **6.6.1.1 Patients continuing on AZD2281**

[figure not shown]
There will be a final data cut-off defined as the time when all patients receiving AZD2281 have been followed for a minimum of 3 months of monotherapy AZD2281 following combination treatment, or there are no more patients remaining on treatment in the study; whichever is the earlier date. At this time point, the clinical study database will close to new data. Patients are however permitted to continue to receive study treatment beyond the closure of the database if, in the opinion of the investigator, they are continuing to receive benefit from treatment with AZD2281. Patients continuing on study treatment will be followed for core safety assessments only (haematology, clinical chemistry, AEs/SAEs and concomitant medications, IMP dosing details).

For patients who do continue to receive treatment beyond the time of this data cut-off, investigators will continue to report all SAEs to AstraZeneca Patient Safety until 30 days after study treatment is discontinued, in accordance with Section 5.10.4 (Reporting of Serious Adverse Events). Additionally as stated in Section 5.10.3 (Recording of adverse events), any SAE or non-serious adverse event that is ongoing at the time of this data cut-off, must be followed up to resolution unless the event is considered by the investigator to be unlikely to resolve, or the patient is lost to follow-up.

Patients continuing on monotherapy AZD2281 at the data cut-off should attend visits according to routine clinical practice but at least every 8 weeks until they meet any discontinuation criteria as per Section 4.4.6.1.

Drug accountability should continue to be performed until the patient stops study treatment completely.

**Figure 4** Flowchart to describe how to handle patients after the data cut-off date

\* Core safety assessments - haematology, clinical chemistry, AEs, concomitant medications

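### The second data cut-off trigger closes the database with no lag, so part or all of the mandated 30-day safety follow-up of the last patients to stop can be lost

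*Protocol*

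**What the plan says.** The synopsis (Data cut-off) gives two triggers, and the earlier one applies. The first is that all patients receiving AZD2281 have at least three months of monotherapy follow-up after the combination. The second is that "there are no more patients remaining on treatment in the study; whichever is the earlier date". Section 6.6.1.1 repeats both triggers and, like the synopsis, goes on: "At this time point, the clinical study database will close to new data". Neither place states a lag or mentions patients who have just stopped.

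Other sections require data after a patient stops:

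- Section 4.2.6: "A final follow-up visit should be conducted 30 days after the last dose of AZD2281".
- Section 5.10.3: "Adverse Events will be collected from time of signed informed consent throughout the treatment period and up to and including the 30-day follow-up period".
- Section 4.4.6.2: "All new AEs and SAEs occurring during the 30 calendar days after the last dose of study medication must be reported".
- Table 4 (visit window ±7 days) and Table 5 ("30 days post discontinuation", ±3 days) both mark haematology and clinical chemistry at this visit.

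The text on the period after the cut-off, in Section 6.6.1.1, covers three things: core safety assessments for patients who continue treatment, SAE reporting for those patients, and follow-up of events already ongoing at the cut-off.

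**The concern.** Under the second trigger nobody is on drug, and the only protocol activity left is the 30-day follow-up of patients who stopped recently. Closing the database on that date discards data that sites are still obliged to collect. The first trigger is different: patients continue beyond the cut-off, and losing some later data is the ordinary price of reporting on time.

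Safety and tolerability are the primary objective. Section 7.4.3 excludes safety data only beyond 30 days from discontinuation, and only for patients who start another anti-cancer therapy, so data inside that window are meant to count.

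The laboratory values have no second route into the analysis. Under Section 5.10.3, deterioration in a protocol-mandated laboratory value becomes an AE only if it is serious or is the reason for discontinuation; otherwise it is summarised from the laboratory data. Section 2 puts the cisplatin platelet and leukocyte nadir at days 18 to 23, with recovery in most patients by day 39. A patient who leaves the combination early in a cycle could therefore reach the nadir during follow-up.

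**Working it through.** The protocol states no figure to reproduce. The check is a day count.

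**Inputs**

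- Closure date: the day nobody remains on treatment (synopsis; Section 6.6.1.1). Call it day 0.
- AE window: 30 days from the last dose (Sections 4.2.6 and 4.4.6.2).
- Visit window: ±7 days (Table 4) or ±3 days (Table 5).
- Intermittent schedules: days 1–10, 1–5, 1–3 or 2–6 of a 21-day cycle (Table 3).
- Longest holds on the combination: 14 days haematological (Section 4.5.3.1), 28 days non-haematological (Section 4.5.3.5).

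**AE days lost.** Let g be the number of days from a patient's last AZD2281 dose to the trigger. Days lost = max(0, 30 − g). For the last patient to stop:

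| Situation at the trigger | g | Days lost of 30 |
|---|---|---|
| Last dose on the trigger date | 0 | 30 |
| Days 1–10 schedule, ends at day 21 | 21 − 10 = 11 | 19 |
| Days 2–6 schedule, ends at day 21 | 21 − 6 = 15 | 15 |
| Days 1–5 schedule, ends at day 21 | 21 − 5 = 16 | 14 |
| Days 1–3 schedule, ends at day 21 | 21 − 3 = 18 | 12 |
| Days 1–10 schedule, then 14-day hold | 11 + 14 = 25 | 5 |
| Days 1–5 schedule, then 14-day hold | 16 + 14 = 30 | 0 |
| Continuous dosing, full 28-day hold | 28 | 2 |

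The rows with g above 0 assume that a patient counts as on treatment until the cycle or the hold ends. The protocol does not say so explicitly. The same formula applies to any other patient whose last dose fell within 30 days before the trigger.

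**30-day laboratory sample.** The earliest permitted visit is 30 − 7 = 23 days after the last dose (Table 4) or 30 − 3 = 27 days (Table 5). It can precede closure only if g is at least 23 or 27. With g between 11 and 18, the earliest combination-phase visit is still 23 − 18 = 5 to 23 − 11 = 12 days after closure. The sample is then lost even though part of the AE window is kept.

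**Number of patients.** When last dose and end of treatment coincide, at least the last patient is affected: 1 of the 60 expected, or 1.7%. The protocol gives no accrual pattern or expected time on treatment. The number of others still in their window, and the chance that the second trigger comes first, therefore cannot be derived from it.

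**When the second trigger can come first.** If the first trigger is read as referring to patients still on drug, the second can precede it only if the last patient stopped while on the combination or with under three months of monotherapy. Otherwise the first would already have been met. On that reading the lost data come from recent combination exposure.

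**The case against.** The best counter-argument is that same-day closure is not the only reading. Section 5.10.3, on post-follow-up events, explains completion of study treatment as the point after any scheduled post-treatment follow-up has ended. Section 6.6 ends the study at the last visit of the last patient. The specific duties in Sections 4.2.6, 4.4.6.2 and 5.10.3 plainly require the data, Section 4.5.7 takes concomitant medications in the CRF up to the 30-day date, and Section 6.7 leaves validation to a Data Management Plan. Figure 4, on handling patients after the cut-off, is missing from the copy reviewed and could contain the exception.

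Part of this stands. The intention to collect is clear, and Figure 4 may settle the matter. But the cut-off rule speaks of patients on treatment, not of treatment completion. It lets patients go on receiving drug after closure, and it ties closure to the same time point. None of the other sections supplies a lag, so the conflict remains on the visible text.

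Two supporting details carry little weight. Section 4.5.3.9 ends the CRF recording of dose changes at the data cut-off, and Table 11 lists the cut-off before the final last visit. Both fit the first trigger equally well.

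A reader might also infer that the last patient always loses the whole 30 days. The documents do not support that. The AE clock runs from the last dose and the trigger runs from leaving treatment, and intermittent dosing or holds can separate the two by weeks.

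**Conclusion.** The point holds as a minor inconsistency. Under the second trigger the literal rule shuts the database before the required 30-day follow-up is complete for the last patient to stop and for anyone else still in that window. The loss for the last patient runs from 30 of 30 days, when last dose and end of treatment coincide, down to possibly none. The data at risk are new non-serious AEs and the 30-day laboratory values, for a small number of patients. This rests on taking the closure wording at face value and on Figure 4 containing no exception.

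A reader might infer that important safety signals or the dose decision are at risk. They are not. Section 5.10.4 requires every SAE to be reported, and the serious-event guidance in Appendix B counts neutropenia or anaemia needing transfusion as an example of a serious event. Section 6.6.1.1 has ongoing AEs followed. DLTs are assessed in cycle 1, so DLT and MTD are unaffected, as are PK and ORR. All analyses are descriptive. Nor do the documents support any estimate of how likely the second trigger is or how many patient-days would be lost in total.

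**What to change.** In the synopsis (Data cut-off) and Section 6.6.1.1, keep both triggers and add one sentence. It should say that the database closes to new data only after the 30-day follow-up visit, including its permitted window, of every patient who discontinued on or before the trigger date. Patients continuing on AZD2281 stay under the existing text. If Figure 4 already allows for this, align the two text passages with it.

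The cost is a later closure: at most 30 + 7 = 37 days after the trigger for patients on the Table 4 schedule, or 30 + 3 = 33 days for those on the Table 5 monotherapy schedule. No visit or sample is added, because the 30-day visit is already required.
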